9.0 Data and Safety Monitoring Plan

9.1 Periodic evaluation of data

Adverse event reporting will be reviewed monthly at departmental meetings while this study continues. Annual reports will be made to the Penn State IRB as per the current protocol.

9.2 Data that are reviewed

Adverse events are defined as unfavorable medical changes that occur during or after the study initiation, that may or may not be related to or caused by study participation. The intensity of the event will be evaluated and recorded as one of the following:

- (1) Mild intensity events may or may not be volunteered by the patient. The patient is aware of the event but it is easily tolerated.
- (2) Moderate intensity signifies discomfort sufficient to interfere with normal activities. A change in therapy may or may not be indicated.
- (3) Severe intensity side effects are almost always brought up by the patient, definitely interfere with functioning, and require a medical intervention.

The study team will be required to assess for adverse events throughout study. In general, this will require a description of the event in sufficient detail to allow for a complete medical assessment of the case and independent determination of possible causality. Information on other possible causes of the event, including concomitant medications and illnesses, must be provided. The investigator's assessment of causality must also be provided. The certainty of the relationship of the event to study participation will be recorded as "Possible Related" or Not Possibly Related." The situation surrounding the event should be assessed to determine whether it is related to the study.

Please refer to Section 3.3.1. Criteria for Removal from Study

9.3 Method of collection of safety information

Study data will be managed using RedCap, a secure web application designed to support data capture for research studies. Well-designed data collection forms will be developed to minimize data collection and recording errors; forms will be designed to collect longitudinal and cumulative information regarding adverse events and concomitant medication usage.

Adverse events will be categorized and patients experiencing adverse events during the treatment will be recorded in RedCap. Patient's will be potentially removed from the study if deemed medically necessary. The principle investigator and IRB will be notified immediately of serious adverse effects.

9.4 Frequency of data collection

Data collection will begin immediately upon enrollment.

9.5 Individuals reviewing the data

The Principal Investigator will receive immediate notification of all serious events, and a regular report summarizing recruitment and all other adverse events. The required offices will be notified immediately of SAEs as per our safety plan and a summary of the reported adverse events will be presented per policy.

9.6 Frequency of review of cumulative data

Data will be reviewed every 6 months.

9.7 Statistical tests

N/A

9.8 Suspension of research

The study participant will be withdrawn and/or the study will be stopped at any time if there are any serious, life threatening adverse events that occur as a result of administration of the test drug. The principal investigator or another licensed professional will be available 24/7 hours to determine the severity and causality of the reported adverse event.

10.0 Risks

Cannabidiol is generally well tolerated with a good safety profile. In clinical trials, a wide range of oral dosages have been used ranging from 1.5-800mg/day.¹⁰

Common risks of Cannabidiol include decreased appetite, somnolence, fatigue, sleep disorder (insomnia), diarrhea, hypersensitivity reactions (rash), infection and liver dysfunction. Because trials are conducted under widely varying conditions, the adverse events observed in one trial cannot be directly compared to the rates in our trial or in observed practice.

Cannabidiol has been associated with dose related elevation of liver transaminases; these effects typically took place within the first 2 months of treatment. Resolution occurred in one third of patients with continuation of medication and without dose reduction; approximately two third resolved with cessation or reduction of the drug. The majority of these cases took place with concomitant use of valproate and to a lesser degree, clobazam. In patients taking an oral solution at a dose of 10mg/kg/day, there was a 1% risk of elevated transaminase levels (elevated three times the upper normal limit), compared with 17% taking a dose of 20mg/kg/day.¹⁶ These dosages are significantly higher than our planned dosages.

Other serious side effects include suicidal ideation and this would result in removal from the study. Less common effects include weight loss, decreases in hemoglobin and hematocrit, and a reversible increase in creatinine in healthy adults.¹⁶

Risk of Norethindrone: Serious adverse reactions with the use of norethindrone are: (1) stroke (2) deep vein thrombosis (3) pulmonary embolism (4) myocardial infarction (5) retinal vein thrombosis. Adverse reactions commonly reported by norethindrone users are: irregular uterine bleeding, nausea, breast tenderness, and headache. Worsening or persistent migraines will result in cessation of study drug.

Pregnancy Risks: Subjects will be required to be non-pregnant at the start of this study. They will also be required to use contraception throughout their participation time. There is currently no adequate data on the developmental risk associated with use of CBD in pregnant women. Administration of CBD to pregnant animals demonstrated an increased risk of fetal toxicity (increased mortality, decreased fetal weight/growth, delayed sexual maturation, long-term neurobehavioral changes). These effects were observed at levels 7-16Xs the recommended maximum level in humans at 20mg/kg/day.¹⁷ At high doses, there was also noted to be an increased risk of structural malformation, adverse effects on male reproductive organs, and fertility. In the case of an inadvertent pregnancy, the study participant will be immediately withdrawn from the study.

Risk of Drug Interactions:

Data from the Epidiolex trials demonstrate significant drug interactions. Co-administration of CBD with certain home medications may result in lower efficacy or high potency of either the CBD or a subject's current medication. These primarily involve Cytochrome P450 Inducers and Inhibitors as well as Substrates of uridine 5'-diphospho-glucuronosyltransferase (UGT) enzymes.

- 1. Co-administration of CBD with a moderate to strong inhibitor of CYP3A4 or CYP2C19 may increase plasma concentration levels. This may result in higher than anticipated levels of CBD.
 - a. Weak inhibitors of CYP3A4 include: amiodarone
 - a. Moderate inhibitors of CYP3A4 include: moclobemide, erythromycin, fluconazole, , diltiazem, verapamil, delavirdine, amprenavir, fosamprenavir, conivaptan.
 - b. Strong inhibitors of CYP3A4 include: Clarithromycin, telithromycin, nefazodone, itraconazole, ketoconazole, atazanavir, darunavir, indinavir, lopinavir, nelfinavir, ritonavir, saquinavir, tipranavir.
 - c. CYP3A4 and CYP2C19 inhibitors of unknown potency include: miconazole and chloramphenicol
 - d. Strong inhibitors of CYP2C19 include: fluconazole, fluoxetine, fluvoxamine, ticlopidine, , moclobemide
- 2. Co-administration of CBD with a strong inducer of CYP3A4 or CYP2C19 may result in lower than expected plasma concentration levels of CBD.
 - a. Strong inducers of CYP3A4: enzalutamide, apalutamidz, phenytoin, carbamazepine, and St. John's wort.
 - b. Moderate inducers of CYP34A or CYP2C19 include: rifampin, rifapentine, efavirenz, phenobarbitol
 - c. Glucocorticoids, , , topiramate, carbamazepine, modafinil, , , oxcarbazepine, nevirapine have an unspecified potency
- 3. There do exist a number of CYP2C19 inducers of weak or unspecified potency that include modafinil, , prednisone, aspirin, norethindrone, but currently none are considered strong inducers of CYP2C19

- 4. In vivo data demonstrates co-administration of CBD increases concentration of CYP2C19 substrates
 - a. CYP2C19 substrates include amitriptyline, citalopram, clomipramine, diazepam, imipramine, phenytoin, omeprazole, R-warfarin, lansoprazole.
- 5. In vitro data suggest a potential reduction in substrates of CYP2C8 and CYP2C9 (e.g. phenytoin) as clinically appropriate. There is potential for both inhibition and induction by CYP1A2 and CYP2B6 substrates/
- 6. In vitro data suggest a reduction in substrates of UGT1A9 and UGT2B7 as clinically appropriate.
 - a. UGT1A9 substrates examples include diflunisal, Propofol, fenofibrate, etodolac, indomethacin, sorafenib
 - b. UGT2B7 substrates examples include gemfibrozil, lamotrigine, morphine, lorazepam, diclofenac, ibuprofen, naproxen

Given the unknown effects of the intended CBD dosages and its interactions with the above medications, we will not plan to make dose adjustments as there would be scant information guiding those adjustments. Patients will be monitored per protocol for adverse events at their visits and with routine bloodwork. They will be be removed from the study if they meet criteria outlined in 3.3.1.

Each study participant will be watched carefully for side effects, particularly if there are medication known to commonly affect liver function, however, doctors do not know all the discomfort and risks that may occur. With all drugs there is the possibility of complications and side effects that are not known at the time. These may be mild or serious, and in some cases may be very serious and permanent. Though it is an uncommon event, there is a risk of unexpected allergic reaction to the study drug which may include hives, rash, swelling or difficulty breathing. If one of the mentioned symptoms appears, subject will be advised to stop taking the study drug (s) and seek immediate medical help.

The study participants will be advised to contact the study doctor or staff with any questions or concerning symptoms.

Risk of Standard of Care medications: Patients will receive standard medications to help prevent and control their endometriosis related pain such as tylenol, ibuprofen and oxycodone. The study doctor can discuss the risks associated with these medications.

Risk of Randomization: The patient will be assigned to a treatment program by chance. The treatment received may prove to be less effective or to have more side effects than the other research treatment(s) or other available treatments.

Risks of standard venipuncture: The discomfort associated with removing blood by venipuncture (by needle from a vein) is a slight pinch or pin prick when the sterile needle enters the skin. The risks include mild discomfort and/or a black and blue mark at the site of puncture. Less common risks include a small blood clot, infection or bleeding at the puncture site, and on rare occasions fainting during the procedure

Risk of Loss of Confidentiality: There is a slight risk of confidentiality associated with participation in this study. To mitigate this risk, all subjects will be assigned a unique study ID that will be used throughout the study to identify each subject. The list linking identifiable information from the study ID will be maintained in the REDCap database designed for this study. REDCap uses secure passwords and access to the database will be restricted to study personnel.

Risk to Others: Given the route of the drug, there will be minimal to no risk to others who are not subjects. The subjects will be advised to keep this drug in a locked and secure space, away from children and/or adults that may come in contact with this drug.

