3.3 Early Withdrawal of Subjects

3.3.1 Criteria for removal from study

Subjects will be removed from the study for safety reasons. Subjects will be evaluated for potential negative reactions to study medications at each visit. Additionally, subjects will be advised to contact the study team immediately with any new negative symptoms.

Known severe adverse events of the study drugs will result in the immediate cessation of the study drugs and removal from the study.

- 1. Severe adverse events of NETA include:
 - a. (1) Stroke (2) Deep Vein Thrombosis (3) Pulmonary Embolism (4) Myocardial Infarction (5) Retinal Vein Thrombosis.
 - b. Worsening or persistent migraines will result in cessation of the study drug and therefore, removal from the study.
- 2. Serious adverse events associated with CBD include:
 - a. (1) Suicidal ideation (2) Liver Dysfunction resulting in hepatic failure, hepatic pain that limits self-care activities of daily living, or acute liver damage as measured by LFTS (elevations in ALT or AST > 3 times the ULN and for ALP or TBL > 2 times the ULN)

In the case of an inadvertent pregnancy, the study participant will be immediately withdrawn from the study.

Other adverse events will be monitored and may result in cessation of the study drug and subject withdrawal from the study as determined by the clinical investigator. When possible, we will use the definitions described by the NIH's Common Terminology Criteria for Adverse Events (CTCAE), Version 5, subjects meeting criteria for a Grade 3 CTCAE will be withdrawn from the study if they can be attributed to the study drug. If causality cannot be determined, it will be attributed to the study drug.

Examples:AnemiaGrade 3Hb < 8.0	DiarrheaGrade 3Increase of \geq 7 stools per day over baseline

Withdrawal of consent at any time during the study period will also constitute the withdrawal of a study subject.

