Patient will be educated on possible adverse events and concerning symptoms. If they have any of the following, they will be advised to stop the medications and contact the study investigator and/or the clinician on call to determine if they require a formal assessment: (1) Shortness of breath or difficulty breathing (2) chest pain (3) visual changes (4) persistent headache (5) severe abdominal pain (6) extensive mouth sores (7) persistent dizziness or lightheadedness (8) unilateral calf pain

Patients will be educated about the symptoms and signs of a DVT/PE and ways to reduce this risk.

Patients will also be educated about the risks of unintended pregnancy as described in the informed Consent. At the time of informed consent, the following will be reviewed with the subject:

Although norethindrone at certain dosages is approved for the indication of contraception. At the dosages this study will use, it is not indicated for this use. Therefore, you will be required to use an acceptable form of contraception during this study unless:

- 1. You have had both of your tubes tied
- 2. Have sex with a man who had a vasectomy at least 6 months ago
- 3. If you do not have sex with men
- 4. You have had a hysterectomy (removal of your uterus)

Acceptable methods include:

- 1. Male Condom: Use prior to intercourse. If using lubricant, choose a water soluble or silicone based as an oil-based lubricant can break down latex condoms.
- 2. Female Condom: Can be inserted up to 6 hours prior to intercourse; it is acceptable to use with lubricants and latex allergies.
- 3. Diaphragm with spermicide: Insert into the vagina so that it covers the cervix. Place spermicide on the diaphragm and around the edges prior to insertion. (Fitted by a healthcare provider)
- 4. Cervical cap with spermicide: Similar to the diaphragm, but smaller. Avoid this method if you have delivered a baby, as it is much less effective.
- 5. Vaginal sponge that contains a spermicide: Insert into the vagina before intercourse. Avoid leaving in the vagina for a prolonged period of time > 24 hours. Avoid this method if you have delivered a baby, as it is much less effective.
- Copper IUD, Progesterone IUD No methods above are 100% effective at preventing unintended pregnancy even with perfect use.

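### For difficulty breathing, section 7.2.3 puts a call to study staff before any assessment, while section 10.0 sends the participant straight to medical help, and nothing says which comes first

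*Combined protocol and SAP*

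**What the plan says.** Two parts of the protocol tell a participant what to do if she has trouble breathing.

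- **Section 7.2.3, Patient Education.** A numbered list of eight warning symptoms begins "1) Shortness of breath or difficulty breathing (2) chest pain". For any of them she is advised to "stop the medications and contact the study investigator and/or the clinician on call to determine if they require a formal assessment". The same text adds: "Patients will be educated about the symptoms and signs of a DVT/PE and ways to reduce this risk".
- **Section 10.0, Risks.** The protocol warns that "there is a risk of unexpected allergic reaction to the study drug which may include hives, rash, swelling or difficulty breathing". The instruction that follows is: "If one of the mentioned symptoms appears, subject will be advised to stop taking the study drug (s) and seek immediate medical help". The text then closes with general advice: "The study participants will be advised to contact the study doctor or staff with any questions or concerning symptoms".

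Two other sections bear on the point. Section 3.3.1 asks participants to contact the team immediately about any new negative symptom, and names the severe events of norethindrone acetate (NETA) as "1) Stroke (2) Deep Vein Thrombosis (3) Pulmonary Embolism (4) Myocardial Infarction (5) Retinal Vein Thrombosis". Section 9.8 provides for the principal investigator or another licensed professional to be available at all hours to judge the severity and causality of a reported event.

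**The concern.** One symptom carries two next steps. Under 7.2.3 the participant telephones, and staff decide whether she needs to be assessed at all. Under section 10.0 she goes to care without waiting for that decision. A participant or coordinator working from 7.2.3 alone could put telephone triage ahead of care for a symptom that the protocol elsewhere treats as needing immediate attention.

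Patient safety is what is at stake. Breathlessness may signal an allergic reaction to the study oil, the setting of the section 10.0 sentence. It may also signal pulmonary embolism, which 3.3.1 lists as a severe NETA event, and every arm takes NETA. In either case a delay could matter, and she should be given one instruction.

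**Working it through.** No arithmetic beyond a count applies, and the plan has no figure to reproduce. The check compares the two texts.

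**Step 1. Line up the symptoms.**

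| Symptom | 7.2.3 Patient Education | 10.0 Risks |
|---|---|---|
| Difficulty breathing | item 1: stop, then call so staff can decide on assessment | stop, then immediate medical help |
| Items 2 to 8 (chest pain, visual changes, headache, abdominal pain, mouth sores, dizziness, calf pain) | stop, then call | not in the allergic-reaction list |
| Hives, rash, swelling | not in the list | stop, then immediate medical help |

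Section 7.2.3 has 8 items and section 10.0 has 4 symptoms, with 1 in common. That leaves 8 − 1 = 7 items in 7.2.3 with no competing instruction, and 4 − 1 = 3 symptoms that appear only in section 10.0.

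**Step 2. Compare the actions for the shared symptom.** Both texts stop treatment. They part at the next step. In 7.2.3 the stated purpose of the contact is to find out whether a formal assessment is needed, so assessment depends on the call. In section 10.0 care is sought at once.

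**Step 3. Ask whether the settings separate them.** Section 10.0 speaks of allergic reaction and 7.2.3 of warning symptoms in general. However, section 10.0 is triggered when any one of its symptoms appears, not by a diagnosis. A woman at home cannot tell an allergic cause from an embolic one, so both instructions apply to her.

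**Step 4. Look for a sentence that sets the order.**

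- Section 3.3.1 says to contact the team immediately. It does not mention seeking care first.
- Section 9.8 makes a clinician available at all hours, but to judge an event that has already been reported.
- The closing sentence of section 10.0 repeats the advice to contact staff, without placing it before or after medical help.

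None of the three says which instruction governs.

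**The case against.** The strongest reply is that the two texts are compatible. Neither forbids the other's next step, 7.2.3 does not tell her to wait for an answer before seeking care, and section 10.0 itself follows immediate help with advice to contact staff. Read together they can mean: stop, get help, notify. The telephone route is also well supported, because 7.2.3 names the on-call clinician as well as the investigator and 9.8 provides cover at all hours. Women with a history of deep venous thrombosis or pulmonary embolism are excluded under 3.2.

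Much of this stands. The defect is an unstated order, not two commands that cannot both be obeyed, and the cover shortens any delay. What survives is that 7.2.3 gives the call the job of deciding whether assessment is needed. Someone following that sentence alone could reasonably wait for the answer. The exclusion lowers the risk of embolism but does not abolish it.

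A reader might infer three further things that the documents do not support.

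- **That it is unclear whether NETA stops for this symptom.** Section 7.1 describes the dispensed medication as both NETA and CBD, so the medications to be stopped in 7.2.3 most naturally include NETA. Section 3.3.1 likewise treats NETA as one of the study drugs when it says "Known severe adverse events of the study drugs will result in the immediate cessation of the study drugs and removal from the study" and then lists the NETA events.
- **That hives, rash and swelling are mishandled, or should also stop NETA.** Their absence from the 7.2.3 list is an omission, since section 10.0 and the general advice in 3.3.1 already cover them. Section 10.0 describes a reaction to the study drug and lists rash as a common CBD risk. A rule to stop NETA for any rash has no clear basis and would interrupt the background therapy of every arm.
- **That participants will in fact receive two instructions.** They act on consent and education material. The consent pages were not available and may already resolve the point.

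**Conclusion.** The point holds for one symptom. The protocol gives difficulty breathing two different next steps and no order between them, and on its own wording 7.2.3 allows telephone triage to come before care. This affects 1 of the 8 items in the 7.2.3 list.

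It is a minor safety clarification. No size of risk is claimed, because the documents give no rate of breathlessness or allergic reaction at the 10 mg and 20 mg doses. Sample size, endpoint and analysis are unaffected. The conclusion rests on the protocol text alone and on the premise that a participant cannot identify the cause of her breathlessness. If the consent material already tells her to seek help first, what remains is to bring 7.2.3 into line with it.

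**What to change.** In the Patient Education text of 7.2.3, take shortness of breath or difficulty breathing out of the stop-and-call list and give it its own sentence: stop the medications, seek medical help immediately, then notify the study team. This matches the action section 10.0 already prescribes. The other seven items can stay as they are, because section 10.0 gives no competing instruction for them. No new NETA rule for hives, rash or swelling is needed. Check the consent form and any participant handout for the same wording.

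The cost is a short wording amendment, with no new visit, procedure or participant. The downside is possibly a few extra urgent visits for breathlessness that turns out to be harmless.

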11.0 Potential Benefits to Subjects and Others

11.1 Potential Benefits to Subjects

The potential benefits to a subject may be a decrease in endometriosis related pain and narcotic use and an improved quality of life.

